8.1.2 Treatment Compliance

Summary (descriptive) statistics will be presented for the number of OmniPods applied by each patient and the treatment compliance during the patient's actual treatment period, defined as the actual days of treatment exposure divided by the patient's total treatment exposure duration. The actual days of treatment exposure is the sum of the durations of individual applications. For each OmniPod application, the duration is calculated as: date of next application — date of current application, or 3, whichever is smaller. For the last application, it is equal to 3.

.

9 Efficacy

A Bayesian adaptive design is adopted to address the following objectives:

- 1. Demonstrate superiority of the pooled middle and high doses over placebo
- 2. Evaluate the dose-response relationship

The adaptive design includes two interim analyses, conducted after approximately 9 and 12 patients per arm enrolling in the study, respectively. Each interim analysis provides opportunities for stopping the trial early due to efficacy success utilizing the group sequential strategy or due to efficacy futility through Bayesian predictive probability of success. Furthermore, it allows the low dose to be dropped following the interim look if it shows a much lower response rate compared with the middle and high doses.

Each interim analysis will result in one of the following outcomes:

- 1. Continue the trial with all arms
- 2. Continue the trial without the low dose
- 3. Declare early success, but continue the trial without placebo
- 4. Declare early success and stop the trial (both placebo and low dose dropped)
- 5. Stop the trial for futility

When the primary efficacy analysis is not successful at the interim analysis, and if the ovulation rate in the low-dose arm is sufficiently low, satisfying

$$R_{low} \le (R_{high+middle}) - 0.2, \tag{1}$$

then the trial will continue without the low dose, resulting in outcome #2 above. Note that R_{low} and $R_{high+middle}$ in the inequality (1) above are the observed ovulation rates in the low dose arm and the combined middle- and high-dose arms, respectively. However, if inequality (1) is not satisfied, then the trial will continue with all arms (outcome #1).

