Conversely, when success on the primary efficacy analysis is declared at an interim analysis, if the response rate in the low-dose arm meets the condition in inequality (1), then the trial is completed at this point (outcome #4) with dose selection performed using the ED80 rule (see below).

In the case the primary efficacy analysis is successful, but the response rate in the low-dose arm is within 20% from the combined low- and high-dose success rate, the trial is not stopped immediately. Rather, the trial will continue to enroll additional patients into the low-, middle- and high-dose arms to further assess dose responses (outcome #3).

Finally, the trial may terminate (outcome #5) as a result of a low predictive probability of success (<0.05) given the data collected at the interim analysis.

At the end of the study, for a trial that achieves efficacy success, the dose to be selected is the ED80 dose, defined as the lowest dose that retains at least 80% of the largest treatment effect, i.e.

$$(R_{ED80} - R_{placebo}) \ge (R_{maximum} - R_{placebo}) \times 0.8, \tag{2}$$

where $R_{maximum}$ is the observed ovulation rate in the most effective dose arm, $R_{placebo}$ is the observed ovulation rate in the placebo arm, and R_{ED80} is the observed ovulation rate in the selected dose arm.

A flow diagram is presented in Figure 1 of Section 15.2.1 to illustrate the decision tree for the two-interim adaptive design. Further details, such as the criteria for efficacy success using the group sequential method, the Bayesian predictive probability of future success to determine futility, the

rationales behind the 20% threshold to drop low dose, the ED80 dose-selection rule and dose-response evaluations are described in Section 9.2.1.1. Simulation results to assess operating characteristics of the design are given in Section 15.2.

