9.2.1.1 Bayesian Adaptive Design Rules

This section provides details for the decision rules to be implemented in the Bayesian adaptive study design.

Success criterion using group sequential strategy

To account for the multiplicities introduced by early success interim analyses, Pocock boundaries are used. Thus, the success threshold at each analysis corresponds to a nominal p-value < 0.0131 to maintain an overall one-sided type I error rate of 0.025.

The simulation results in Figure 13 for Scenario 7 in Section 15.2.3, as well as the justification provided in Section 15.2.4, show that the type I error is well controlled under the null hypothesis using the success boundary.

Futility criterion

Given the data collected at each interim time point, we compute the Bayesian predictive probability that the primary analysis will meet the success threshold once all arms have n = 15 subjects. If the predictive probability is less than 0.05, then the trial will be declared as a failure and terminate at this point due to futility.

The Bayesian predictive probability is calculated in the following fashion. First, for each arm d, we determine the number of future subjects required to complete the study, m_d . Then, the number of future responders occurring in arm d, Z_d , is generated from a Beta-Binomial distribution:

$$(Z_d | n_d, x_d) \sim BetaBinomial(m_d, a + x_d, b + n_d - x_d),$$

where n_{d} , x_{d} are the numbers of subjects and responders in arm d observed at interim analysis, and a non-informative prior Beta distribution with parameters a = 0.5 and b = 0.5 is used independently for each arm.

A large number of predicted values are sampled from the Beta-Binomial distribution for each arm, resulting in 1000 "complete" datasets. The predictive probability of eventual trial success is then the proportion of these complete datasets for which the primary analysis success threshold is met (p-value < 0.0131).

Dropping the low dose

If the observed response rate for the low dose meets the condition in inequality (2), then low dose will be dropped from additional enrolment, should the trial need to continue with the high dose, middle dose and placebo to assess the primary efficacy endpoint at the next analysis timing.

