The remaining sample size that had been planned for the low dose will be reallocated among the remaining arms. Thus the sample size for the placebo, middle, and high doses may either be 9, 12, 15, 16, or 17 subjects, depending on whether early success is declared, and whether low dose is dropped at the first or second interim analysis.

The 20% threshold to drop low dose is chosen based on the ED80 dose-selection rule, as the maximum of the most effective treatment effect can reach 100% (with the success rate in the placebo group expected to be close to 0). It ensures that when the threshold is met, the low dose does not qualify as the ED80 dose. Furthermore, we present in Table 3 below the Bayesian predictive probabilities of selecting low dose as ED80, should it proceed to a later analysis, for a range of borderline interim analysis observations where the 20% threshold is just met. A non-informative prior Beta (0.5, 0.5) is used for all treatment arms and 10000 predictions were generated. The results show that such probabilities are small: <10% in all cases and <5% in all but three cases. Therefore, 20% is a justifiable choice for the threshold to drop low dose early.

Table 3 Bayesian Predicted Probability of Selecting Low Dose as ED80 at a Later Analysis when Low Dose was Dropped Early

		rxnary	ois when L	in Dust was	, Dropp	cu Larry
N per arm	N per arm	Observe	d n (%) of su	ccesses at	Diff*	Probability of
at interim	at later	interim analysis			(%)	selecting low dose as
analysis	analysis	High-dose	Mid-dose	Low-dose		ED80 if continue
						with low dose
9	12	6 (67.8)	4 (44.4)	3 (33.3)	-22.2	0.0207
		5 (55.6)	5 (55.6)	3 (33.3)	-22.2	0.0735
		5 (55.6)	4 (44.4)	2 (22.2)	-27.8	0.0059
		5 (55.6)	3 (33.3)	2 (22.2)	-22.2	0.0062
		4 (44.4)	4 (44.4)	2 (22.2)	-22.2	0.0159
	15	6 (67.8)	4 (44.4)	3 (33.3)	-22.2	0.0304
		5 (55.6)	5 (55.6)	3 (33.3)	-22.2	0.0672
		5 (55.6)	4 (44.4)	2 (22.2)	-27.8	0.0136
		5 (55.6)	3 (33.3)	2 (22.2)	-22.2	0.0201
		4 (44.4)	4 (44.4)	2 (22.2)	-22.2	0.0555
12	15	8 (75.0)	6 (50.0)	4 (33.3)	-25.0	0.0015
		7 (58.3)	6 (50.0)	4 (33.3)	-20.9	0.0231
		7 (58.3)	5 (41.7)	3 (25.0)	-25.0	0.0012
		7 (58.3)	4 (33.3)	3 (25.0)	-20.8	0.0014
		6 (50.0)	5 (41.7)	3 (25.0)	-20.8	0.0211
		6 (50.0)	4 (33.3)	2 (16.7)	-25.0	0.0011
		5 (41.7)	5 (41.7)	2 (16.7)	-25.0	0.0059
		5 (41.7)	4 (33.3)	2 (16.7)	-20.8	0.0173

Diff* is the difference in observed success rates between the low-dose group vs. the pooled high- and mid-dose groups

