In this scenario, all doses are highly effective. The power of the trial exceeds 99%, with most trials declaring early success at an interim. Of the 10000 simulated trials, 9332 trials (93.3%) declared early success at the first interim. Of those, 2782 trials also dropped the low dose at the same time (ending the trial), and 6550 dropped the placebo and continued with only the investigational arms. Of those trials, 570 trials dropped the low dose at the second interim, while the remaining 5980 trials continued to the final analysis with all investigational arms. The average sample size reflects the tendency of trials to declare early success, with the placebo arm having, on average, 9.2 subjects (smaller than the investigational arms). In truth, the low dose is quite effective, so it is rarely dropped, and it is selected as the ED80 in 45.6% of trials.

Statistical Analysis Plan

Trial Outcomes

Pr(Success)	Pr(Early Win)	Pr(Early Futility)
0.999	0.990	0.000

Mean Sample Size

Placebo	Low	Mid	High	Total
9.2	13.1	13.1	13.1	48.6

None	Low	Mid	High
0.001	0.456	0.356	0.188

[figure not shown]
Figure 7 Operating Characteristics for Scenario 1: 0.01, 0.60, 0.65, 0.70

Date: 07 Dec 2017 E-Statistical Analysis Plan-21977; Ver. 1.0 Supersedes: None Page 43 of 59

Scenario 2: 0.01, 0.50, 0.65, 0.75

In this scenario, there is a larger range between the low dose and high dose response rates. The low dose response rate is exactly 20% lower than the combined middle and high doses.

This scenario also has quite high power, and is more likely to stop the trial early due to declaring early success and dropping the low dose. Roughly half of the trials (50.5%) ended at the first interim, with an additional 45% declaring early success at the first interim, but continuing the trial (without the placebo arm). The average sample size tends to be smaller in this scenario, since more trials end early. The middle dose is most likely to be selected as the ED80.

Pr(Success)	Pr(Early Win)	Pr(Early Futility)
1.000	0.994	0.000

Mean Sample Size

Placebo	Low	Mid	High	Total
9.2	11.7	11.7	11.7	44.2

None	Low	Mid	High
0.000	0.182	0.482	0.335

[figure not shown]
Figure 8 Operating Characteristics for Scenario 2: 0.01, 0.50, 0.65, 0.75

Date: 07 Dec 2017 E-Statistical Analysis Plan-21977; Ver.1.0 Supersedes: None Page 45 of 59

Scenario 3: 0.01, 0.20, 0.60, 0.60

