In this scenario, the middle and high doses are equivalent, each having a 60% response rate (less effective than previous scenarios, but still highly effective relative to placebo). The low dose response rate is 40% lower than the combined middle and high doses, so we expect it to be dropped in a large percentage of trials.

In fact, since the pooled middle and high doses are effective and the low dose is inferior to pooled, most trials are able to declare early success and stop the trial early: 76.5% of trials declare success and stop at the first interim, and an additional 14.7% (353+235+885 trials) ended with success at the second interim. There were 459 trials that declared early success at an interim, but continued enrolling the low dose to the final analysis. The middle dose was selected as the ED80 in 72% of trials.

Pr(Success)	Pr(Early Win)	Pr(Early Futility)
0.994	0.958	0.003

Mean Sample Size

mean cample cize				
Placebo	Low	Mid	High	Total
9.7	9.5	10	10	39.2

None	Low	Mid	High
0.006	0.003	0.720	0.271

[figure not shown]
Figure 9 Operating Characteristics for Scenario 3: 0.01, 0.20, 0.60, 0.60

Date: 07 Dec 2017 E-Statistical Analysis Plan-21977; Ver.1.0 Supersedes: None Page 47 of 59

Scenario 4: 0.01, 0.10, 0.40, 0.50

In this scenario, the pooled response rate for the middle and high doses is 45%. This smaller effect is reflected in lower power relative to the previous scenarios.

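### The ED80 selection frequencies in SAP 15.2.3 and the probabilities in SAP Table 3 do not follow the SAP's own definitions; the selection figures are off by up to 5 points

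*SAP*

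**What the plan says.** SAP Section 9 (Efficacy) gives the selected dose as the ED80, "defined as the lowest dose that retains at least 80% of the largest treatment effect". Inequality (2) writes this with a greater-than-or-equal sign on observed rates net of placebo, and Protocol 9.6.1 has the same rule. Nothing in either document says that an exact 80% tie fails.

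SAP 15.2.3 reports ED80 selection frequencies from 10,000 virtual trials per scenario, presented as run under the pre-specified rules. For Scenario 3: "The middle dose was selected as the ED80 in 72% of trials". For the low dose in Scenario 1: "it is selected as the ED80 in 45.6% of trials".

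SAP 9.2.1.1 uses Table 3 to support the 20-point threshold for dropping the low dose. The table is described as a Bayesian prediction with Beta(0.5, 0.5) priors and 10,000 draws. The stated conclusion is that the probability of later selecting a dropped low dose is "<10% in all cases and <5% in all but three cases".

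**The concern.** With 9 to 17 subjects per arm and almost no placebo responders, an effect of exactly 80% of the maximum is a common outcome: 4 against 5, 8 against 10, or 12 against 15 responders. Whether such a tie passes decides which dose is labelled ED80. Dose response is the adaptive design's second objective, and SAP 9.2.1.1 has the ED80 dose marked in the primary efficacy table. If the simulations handled ties differently from the written rule, the SAP misdescribes how often each dose would be chosen. The figures offered in support of the drop threshold would be affected as well.

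**Working it through.** **Inputs** (scenario numbers as in the text of SAP 15.2.3)
- Success: one-sided Fisher p < 0.0131 at each look (SAP 9.2.1.1).
- Looks at 9 and 12 per arm, final at 15, or at 16 or 17 after reallocation.
- Futility: beta-binomial predictive probability below 0.05.
- Low dose dropped if 0.2 below pooled mid+high, inequality (1). The protocol's < and the SAP's ≤ agree, because no tie is possible: 2×low = pooled − 3.6 (n = 9) or pooled − 4.8 (n = 12) has no integer solution. SAP 9.2.1.1 cites inequality (2) for dropping; I assume (1), as in Section 9 and the worked examples.

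**Reproducing the plan first.** The model returns the SAP's Fisher p-values (0.0052, 0.0197, 0.0139), its 118 successful combinations, and Pr(Success) and Pr(Early Win) in Scenarios 1-6 within 0.5 point. Pr(Early Futility) agrees within about 1 point.

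**Selection frequencies** (1-2 million trials per scenario; repeat runs moved these by at most 0.5 point)

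| Scenario, dose | SAP | Ties fail | Written rule |
|---|---|---|---|
| 1 low | 0.456 | 0.467 | 0.491 |
| 2 low | 0.182 | 0.180 | 0.199 |
| 3 mid / high | 0.720 / 0.271 | 0.721 / 0.269 | 0.750 / 0.240 |
| 4 mid / high | 0.451 / 0.458 | 0.448 / 0.464 | 0.501 / 0.410 |
| 5 mid / high | 0.551 / 0.255 | 0.549 / 0.261 | 0.584 / 0.224 |
| 6 mid | 0.095 | 0.090 | 0.099 |

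The Monte Carlo SE of a SAP figure is at most √(0.5×0.5/10,000) = 0.005. The Scenario 4 mid-dose gap is 0.501 − 0.451 = 0.050, about 10 SE. The Scenario 2 gap is 0.199 − 0.182 = 0.017, with SE √(0.182×0.818/10,000) = 0.0039, about 4 SE.

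**Hand check.** Take one pattern at the first look: mid 4/9, high 5/9, placebo 0/9. It is a success (p = 0.0104). The low dose is dropped if low/9 < 9/18 − 0.2, that is, at most 2 responders. The written rule then picks mid; failing ties picks high. The probability is P(mid 4)·P(high 5)·P(placebo 0)·P(low ≤ 2), with P(placebo 0) = 0.99⁹ = 0.9135:
- Scenario 3: 0.0419 × 0.9135 × 0.738 = 0.028
- Scenario 4: 0.0617 × 0.9135 × 0.947 = 0.053
- Scenario 5: 0.0419 × 0.9135 × 0.947 = 0.036

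The gaps between the last two table columns for the mid dose are 0.029, 0.053 and 0.035. This one tie accounts for them.

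**Table 3**, enumerated exactly with no placebo responders. I used the printed counts; two printed high-dose percentages (67.8 for 6/9, 75.0 for 8/12) do not match them, but the difference column does. Plug-in means a binomial with rate (x+0.5)/(n+1). Beta-binomial is the predictive distribution with parameters x+0.5 and n−x+0.5.

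| High/mid/low, from-to | SAP | Plug-in, ties fail | Plug-in, ties count | Beta-binomial, ties count |
|---|---|---|---|---|
| 6/4/3, 9-12 | 0.0207 | 0.0214 | 0.0214 | 0.0330 |
| 5/5/3, 9-12 | 0.0735 | 0.0730 | 0.0767 | 0.0907 |
| 5/4/2, 9-12 | 0.0059 | 0.0060 | 0.0134 | 0.0216 |
| 5/3/2, 9-12 | 0.0062 | 0.0066 | 0.0189 | 0.0298 |
| 4/4/2, 9-12 | 0.0159 | 0.0168 | 0.0594 | 0.0712 |
| 6/4/3, 9-15 | 0.0304 | 0.0234 | 0.0302 | 0.0633 |
| 5/5/3, 9-15 | 0.0672 | 0.0627 | 0.0678 | 0.1053 |
| 4/4/2, 9-15 | 0.0555 | 0.0483 | 0.0560 | 0.0844 |
| 5/4/2, 12-15 | 0.0173 | 0.0042 | 0.0166 | 0.0241 |

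Worked row, 4/4/2 from 9 to 12, plug-in rates 0.45, 0.45 and 0.25. The tie is low 4 against a maximum of 5.
- P(low gains 2 of 3) = 3 × 0.25² × 0.75 = 0.1406.
- For mid or high, P(gain ≤ 1) = 0.55³ + 3 × 0.45 × 0.55² = 0.5748 and P(gain 0) = 0.55³ = 0.1664.
- P(maximum = 5) = 0.5748² − 0.1664² = 0.3027.
- The tie contributes 0.1406 × 0.3027 = 0.0426, and 0.0168 + 0.0426 = 0.0594.

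The SAP's 9-to-12 figures fit the plug-in with ties failing; its figures ending at 15 fit the plug-in with ties counted. Counting ties alone puts four rows above 5% instead of three and leaves all below 10%. With beta-binomial prediction as well, five rows exceed 5%, and 5/5/3 from 9 to 15 is 0.105 (0.102 if future placebo responders are also predicted).

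**The case against.** The strongest reply is that this is a descriptive appendix. Success, early stopping, futility, the low-dose drop and type I error do not use inequality (2), and the SAP sets no target for ED80 selection. That stands. So does the point that the 20-point threshold is argued first from the ED80 rule with near-zero placebo response, with Table 3 only as further support. Unequal arms in the full analysis set would also remove some exact ties.

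The fit is not complete. In Scenario 1, failing ties explains only part of the gap: 0.467 to 0.472 across runs, against 0.456 stated and 0.491 under the written rule. Scenario 6 cannot separate the two readings.

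Two stronger readings are tempting, and the documents do not support them:
- *A rounding fault will make the real analysis pick the wrong dose.* In double precision, 4/9 ≥ (5/9)×0.8 is false, but 0.8×5/9 passes, and the same tie passes at n = 15 and 16. Double precision leaves Scenarios 1 and 2 at their written-rule values, so it does not explain those; a strict inequality does not explain the Table 3 rows ending at 15. The simulations used custom R code that is not shown, and the trial analysis uses SAS. The cause cannot be determined.
- *Ties explain all of Table 3.* They do not. The 13 rows ending at 15 already count ties; their discrepancy comes from the prediction method.

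**Conclusion.** The point holds in limited form. The ED80 frequencies for Scenarios 2-5 are reproduced only when exact 80% ties fail, contrary to inequality (2). The error reaches 5 points and reverses the mid/high ordering in Scenario 4. Scenario 1 is also inconsistent with the written rule, but only partly for this reason. The summary sentence on Table 3 does not hold: ties alone break its second half, and its first half fails under the beta-binomial prediction that the stated prior implies. That breach is narrow, at 0.102 to 0.105 in one row.

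This rests on equal arms at the planned sizes, the decision rules listed above and, for Table 3, no placebo responders at the interim. The written dose-selection rule is itself clear; the defect is in the figures reported for it.

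**What to change.** 1. In SAP 9.2.1.1, state that inequality (2) is evaluated on counts (cross-multiplied where arm sizes differ) or with a stated rounding tolerance, so that exact ties qualify. Apply this in the simulation code and the trial's analysis program.
2. Re-run the ED80 selection tables for all scenarios in SAP 15.2.3 and restate the figures and accompanying text.
3. Recompute Table 3 with ties counted and beta-binomial prediction, or say that a posterior-mean plug-in was used. State the assumed placebo result and rewrite the sentence that summarises the table.

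The cost is a short SAP amendment and a simulation re-run. Conduct, sample size, stopping boundaries and the primary test do not change.

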3.2 Determination of Sample Size

The sample size was determined based on the original fixed parallel group study design. The true ovulation rate for LutrePulse OmniPod SC 20µg, 15µg, 10µg, and placebo was assumed to be 70%, 65%, 60%, and 1%, respectively. Under these assumptions, a sample size of 14 subjects per group (total 56 subjects) will provide at least 80% power to detect differences between LutrePulse OmniPod SC 20µg and placebo, 15µg and placebo, and 10µg and placebo in ovulation rate separately with the stratified one-sided Fisher's exact tests at an overall significance level of 0.025 with the closed testing procedure (Kong et al., 2005). Approximately 60 subjects will be randomized by assuming up to 4 subjects may be ineligible to the Full Analysis Set.

Date: 07 Dec 2017 E-Statistical Analysis Plan-21977; Ver. 1.0 Supersedes: None Page 11 of 59

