9.2 Primary Endpoint(s)

9.2.1 Primary Variable Analysis

The primary efficacy endpoint is the ovulation rate calculated as the proportion of subjects who had at least one post-baseline P4 level ≥ 6 ng/mL or pregnancy confirmed by at least 2 positive serum β -hCG tests or detection of gestational sac on transvaginal ultrasound (TVUS). The denominator will be based on all subjects in the FAS. Subjects who do not have a confirmed pregnancy, or at least one P4 level ≥ 6 ng/mL due to the P4 levels never reaching this threshold, missing data, early withdrawal, or any other reason will be counted as not having ovulation (treatment failure).

The primary efficacy analysis will compare the pooled ovulation rate of LutrePulse OmniPod SC 20 μ g and 15 μ g to placebo. Let $P_{high+middle}$ and $P_{placebo}$ be the underlying ovulation rates in the combined middle- and high-dose arms and the placebo arm, respectively. The hypotheses for the one-sided statistical testing are:

$$H_0: P_{high+middle} \leq P_{placebo},$$

VS.

$$H_0: P_{high+middle} > P_{placebo}.$$

The hypotheses are tested using a stratified one-sided Fisher's exact test (Jung et al., 2014) in the FAS including the randomization scheme as the stratification factor. The SAS PROC FREQ with permutation-based Cochran-Mantel-Haenszel test with exact p-value derived from all possible permutations will be employed for the calculation of p-value for the stratified Fisher's exact test.

Date: 07 Dec 2017 E-Statistical Analysis Plan-21977; Ver.1.0 Supersedes: None Page 21 of 59

Jung has shown that the stratified Fisher's exact test is equivalent to the exact stratified Mantel-Haenszel test when exact p-value is derived from all possible permutations.

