In the third example (Figure 4), the pooled response rate at the first interim is 44.4% (8 total responders, with 3 on the middle dose and 5 on the high dose) versus 0% on placebo. The p-value is 0.0197 which does not meet the early success threshold. The predictive probability of eventual trial success is 86.1%, so the trial does not stop for futility. The low dose response rate is only 22.2%, which is more than 20% lower than the pooled response rate. Thus, the low dose is dropped, and accrual continues on the placebo, middle, and high dose arms.

The second interim occurs when the remaining arms each have 12 subjects. Since the last interim, there is one new responder on the high dose, and no new responders on the placebo or middle dose arms. The p-value for the pooled versus placebo is 0.0139, which is not sufficient to declare early success. The predictive probability is still above the futility threshold, so the trial continues to the final analysis.

Since the low dose was dropped at the first interim with only 9 subjects, the remaining 6 slots that would have been allocated to the low dose have been redistributed to the remaining arms. Thus, each arm at the final analysis has n = 17 subjects rather than n = 15. The p-value for the Fisher Exact test is 0.0011, so the trial meets success at the final analysis. The high dose is selected as the ED80.

[figure not shown]

Figure 4 Simulation results from Example Trial 3

At the first interim of example trial 4 (Figure 5), the response rate is a modest 20-30% on the investigational arms. No responses were observed on the placebo. The trial does not declare early success, but has high enough predictive probability to continue. Additionally, the low dose is not sufficiently lower than the pooled arms to be dropped. Thus, the trial continues enrolling subjects to all arms.

At the second interim, there are n=12 subjects allocated to each arm. No additional responses were observed on the low dose, which had only 2 responders (16.7%). The response rate for the pooled middle and high doses is now 41.7%. Neither the early success nor futility criteria were met. However, the low dose response rate is no longer within 20% of the pooled, so it will be dropped. The 3 remaining slots for the low dose are redistributed so that each remaining arm will receive one additional subject.

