The trial stopped for futility 4.7% of the time (240 trials at the first interim and 232 trials at the second interim). Since the low dose is much lower than the middle and high doses, and since the efficacy of the middle and high doses is lower than previous scenarios, we see more trials here that drop the low dose and continue the trial with only the placebo, middle dose, and high dose. There were 4620 trials that dropped the low dose at the first interim. Of those, 2319 trials met early success at the next interim (thus ending the trial), while 122 of the trials stopped for futility at the next interim and 2179 continued to the final analysis. Thus, for these 2179 trials, the final sample size for the low dose was 9 subjects, while the middle and high doses each had a final sample size of 17 subjects (each arm receiving two extra subjects because of the low dose dropping at the first interim). Additionally, there were 323 trials that continued all arms at the first interim, then dropped the low dose at the second interim. In these trials, the final sample size for the low dose was 12 subjects while the middle and high doses each received one extra subject for a total of 16 subjects at the final analysis.

Pr(Success)	Pr(Early Win)	Pr(Early Futility)
0.910	0.653	0.047

Mean Sample Size

Placebo	Low	Mid	High	Total
12.1	9.6	12.2	12.2	46.2

None	Low	Mid	High
0.090	0.001	0.451	0.458

[figure not shown]
Figure 10 Operating Characteristics for Scenario 4: 0.01, 0.10, 0.40, 0.50

Date: 07 Dec 2017 E-Statistical Analysis Plan-21977; Ver. 1.0 Supersedes: None Page 49 of 59

Scenario 5: 0.01, 0.10, 0.40, 0.40

In this scenario, the middle and high doses are equivalent with a 40% response rate. The low dose is 30% lower than the middle and high doses.

Roughly half of the simulated trials (5185 trials, or 51.9%) dropped the low dose at the first interim, but continued enrolling the other arms. An additional 482 trials (4.8%) dropped the low dose at the second interim. With the high probability of dropping the low dose, the average sample size for the low dose is 9.9 while the middle and high doses tend to have larger sample sizes, since they receive re-allocated subjects from the dropped low dose. The power for this scenario is 80.7%. The probability of early futility is 10.6% (5.5% at the first interim and 5.1% at the second interim).

Pr(Success)	Pr(Early Win)	Pr(Early Futility)
0.807	0.471	0.106

Mean Sample Size

mean cample offe					

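### The power figures in SAP 15.2.3 come from an unstratified Fisher test on all 60 randomized subjects, not the planned stratified FAS analysis; Scenario 5 power is about 79% with no FAS loss and about 74% with the planned loss, against the stated 80.7%

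*SAP*

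**What the plan says.** SAP 9.2.1 (and protocol 9.6.2) tests the pooled 15 µg and 20 µg arms against placebo with a one-sided Fisher exact test, "in the FAS including the randomization scheme as the stratification factor". At all three analyses "the success threshold at each analysis corresponds to a nominal p-value < 0.0131", chosen "to maintain an overall one-sided type I error rate of 0.025".

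SAP 3.3 defines three schemes. The first 15 subjects go 1:1:1 to 10 µg, 20 µg and placebo, with no 15 µg arm. The next 25 go 1:2:1:1 to 10 µg, 15 µg, 20 µg and placebo. The rest go 1:1:1:1. Subjects who discontinue early are not replaced.

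SAP 3.2 plans 14 subjects per group for analysis: "Approximately 60 subjects will be randomized by assuming up to 4 subjects may be ineligible to the Full Analysis Set". FAS membership needs at least 14 days of study drug (SAP 6.2).

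Section 9 of the SAP describes "two interim analyses, conducted after approximately 9 and 12 patients per arm enrolling in the study". SAP 9.2.1.1 gives 9, 12, 15, 16 or 17 subjects for placebo, middle and high dose, depending on early success and on when the low dose is dropped. SAP 15.2.3 reports power by scenario. Under "Scenario 5: 0.01, 0.10, 0.40, 0.40" it says "The power for this scenario is 80.7" per cent. The worked examples in SAP 15.2.2 report results such as "The p-value for the Fisher Exact test is 0.0011, so the trial meets success at the final analysis". Neither subsection mentions strata or FAS exclusions.

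**The concern.** SAP Section 9 points to Section 15.2 for the operating characteristics of the design, and protocol 9.6.2 defers to the SAP for them. If those figures come from a different test on a different set of subjects, they do not describe the analysis that will decide the trial. Two gaps are involved.

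- **Test.** The simulations ignore the strata. The 15 µg arm has nobody in the first scheme, so strata and arms are unbalanced against each other, and the two tests can give different answers on the same totals.
- **Numbers analysed.** The simulated final counts use every randomized subject, although the sample-size section allows for up to four outside the FAS.

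At stake is whether the stated power, early-success and first-look figures can be relied on, above all in Scenario 5, where the stated value is just above 80%.

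**Working it through.** **1. How many subjects the simulations analyse.** With no arm dropped: 15 × 4 = 60. Low dose dropped at the first look: 17 × 3 + 9 = 60. Dropped at the second look: 16 × 3 + 12 = 60. All randomized subjects are counted, with no FAS loss.

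**2. Which test they use.** With no placebo responders and x responders among 2n pooled subjects, the unstratified one-sided Fisher p-value is C(2n, x) / C(3n, x).

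- Example 1, 10/18 v 0/9: 43,758 / 8,436,285 = 0.0052, as stated.
- Example 3, first look, 8/18 v 0/9: 43,758 / 2,220,075 = 0.0197, as stated.
- Example 3, second look, 9/24 v 0/12: 0.0139, as stated.
- The two final p-values, 0.0011 and 0.0205, are the unstratified values for 14/34 v 0/17 and 12/32 v 1/16. These counts are inferred, because the figures are not available.

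The unstratified test also returns the 118 successful outcomes and the type I error of 1.018 × 10⁻¹¹ in SAP 15.2.4.

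**3. What stratification does to the same data.** Assume subjects enter in scheme order. At 9 per arm, scheme 1 then holds five 20 µg and five placebo subjects; scheme 2 holds thirteen pooled active (nine at 15 µg, four at 20 µg) and four placebo. With no placebo responders and a of the x active responders in scheme 1:

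p = [C(5, a) / C(10, a)] × [C(13, x − a) / C(17, x − a)]

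| Responders at first look | Unstratified p | Stratified p for a = 0, 1, 2, 3, 4, 5 |
|---|---|---|
| 8/18 v 0/9 | 0.0197 | 0.0529, 0.0441, 0.0308, 0.0173, 0.0072, 0.0017 |
| 9/18 v 0/9 | 48,620 / 4,686,825 = 0.0104 | 0.0294, 0.0265, 0.0196, 0.0116, 0.0050, 0.0012 |

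No stratified value for 8/18 equals the SAP's 0.0197. Against 0.0131, nine responders always succeed without strata but need at least three in scheme 1 with strata. Eight always fail without strata but succeed with strata if four or five are in scheme 1. So stratification can move the result either way.

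**4. Simulated power.** The two-look design was simulated with exact p-values (stratum hypergeometrics convolved for the stratified test), the low-dose drop rule and Beta(0.5, 0.5) predictive futility below 0.05. Scheme sizes for placebo and 20 µg were 5, 5 and the rest; for 15 µg they were 0, 10 and the rest. Looks were at 9 and 12 analysable subjects per arm. Planned loss means final counts of 14, or 16 or 15 after a low-dose drop.

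Reproduction first: unstratified with 15 per arm, Scenario 5 gives 80.8% to 81.5% (SAP 80.7%) and Scenario 4 about 91% (SAP 91.0%).

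| Scenario | SAP | Stratified, no FAS loss | Stratified, planned loss |
|---|---|---|---|
| 1 (planning rates) | 99.9% | above 99% | 99.7% |
| 3 | 99.4% | about 99.4% | about 99% |
| 4 | 91.0% | about 90.5% | about 88% |
| 5 | 80.7% | about 79% (78.5% to 79.6%) | about 74% (71% to 76%) |
| 6 | 42.8% | about 44.5% | about 40% (40.1% to 41.8%) |

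The 71% to 76% range for Scenario 5 comes from choices the SAP leaves open:

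- 74.0% with futility projected to 15 per arm
- 72.3% with futility projected to 14
- 70.8% if freed low-dose slots are rounded down
- 75.9% with no futility rule

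The loss to 14 per arm alone, with the unstratified test, gives 75.4% to 77.1% with the slots not rounded down. So the FAS loss accounts for most of the fall.

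**5. Early success, 15 per arm, unstratified to stratified.**

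- First look: Scenario 1 about 93% to 91%, Scenario 3 about 82% to 75%, Scenario 5 about 24% to 20%. In Scenario 6 it rises, from 5.1% to 8.1%.
- Both looks: Scenario 4 65.6% to 68.5%, Scenario 5 47.6% to 49.8%, Scenario 6 13.5% to 21.1%. Scenario 1 is unchanged at 99.0%.

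**The case against.** The strongest reply is that 80.7% is correct for the model that was simulated, and that the lower figures only follow from different inputs. That is fair. A reader might infer an arithmetic error, but the number reproduces; what fails is the match between the model and the planned analysis.

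Second, the SAP says up to four subjects may be ineligible. That is an allowance, not an expectation. A reader might infer that Scenario 5 power simply is about 74%, but the documents support that only if the whole allowance is used, one loss per arm. With no loss the shortfall is 80.7 − 79 = about 1.7 points.

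Third, a reader might infer that the trial is underpowered. The documents do not support that. SAP 3.2 sizes the trial on rates of 60% to 70% against 1%, already with 14 per group and a stratified test. The matching Scenario 1 stays above 99%. Scenario 5 is one of several weaker stress cases, and nowhere does the plan commit to 80% power there.

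Fourth, it would be tempting to say that stratification makes every figure worse. It does not: Scenario 6 power rises under stratification alone, and early success over both looks is unchanged or higher in Scenarios 4 to 6.

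Finally, SAP 15.2.4 accepts small departures from the simulation assumptions. It does so for type I error, which is not disputed here; it says nothing about power.

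**Conclusion.** The point holds as a mismatch between the reported operating characteristics and the planned analysis. The identification of the test is firm, because the published p-values with known counts match only the unstratified calculation. In Scenario 5 the difference from the stated power runs from about 1.7 points with no FAS loss to 80.7 − 74 = about 6.7 points with the full allowance. In Scenario 4 it is about 0.5 to 3 points. Scenarios 1 and 3 barely move.

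These sizes rest on enrolment in scheme order, looks counted in analysable subjects, and, for the lower figures, exactly one FAS loss per arm. The SAP settles none of these. Its Section 9 times the looks by enrolment and its Section 11 by completion, and it does not say whether the futility projection is stratified. The direction in Scenarios 4 and 5 is clear; the exact values are not. The figures should be corrected, but the validity of the trial does not depend on it.

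**What to change.** Re-run SAP 15.2.3 with the stratified exact test and the actual scheme sizes (15, 25, rest). Use FAS counts in two versions: no loss, and the planned 14 per arm. Replace the stated power, early-success and first-look figures with the re-run values, and recompute the example p-values or label them as unstratified illustrations. State the assumptions used: whether looks count enrolled, completed or FAS subjects, how freed low-dose slots are reallocated, and whether the futility projection uses strata.

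The cost is a simulation re-run and a short SAP edit. Some figures will be lower (power in Scenarios 4 and 5, and first-look success in Scenarios 1, 3 and 5), and some early-success figures will be higher. No extra subjects are needed, and sample size, alpha and decision rules stay as they are.
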